Hypotheses: We hypothesize that the DPR group will have a more benign hospital course as measured by time to full enteral feeds of 100 kcal/kg/day. We will also assess time to abdominal wall closure, time on TPN, length of hospital stay and intestinal motility post-closure using bedside ultrasounds. Secondly, we hypothesize that there will be no deleterious effects related to introducing the peritoneal dialysis solution into the silo.

Study Objectives

Primary Objectives:

1. To demonstrate that subjects treated with DPR will have a more benign hospital course as measured by time to full enteral feeds. The primary outcome measure will be time to full feeds of 100 kcal/kg/day. Secondary outcomes will include length of time until abdominal wall closure, time on TPN, time to intestinal motility, and total days in the hospital.
2. To demonstrate that the use of DPR in neonates with gastroschisis treated with staged silo closure will result in no significant changes in commonly measured clinical and laboratory safety parameters. This will be measured with more frequent clinical and laboratory assessments for the DPR group. Vital signs and strict intake and output will be monitored every 6 hours for 48 hours after the maximum dialysate infusion volume has been reached, then every 12 hours. Sodium, potassium, blood glucose and lactate levels will be monitored every 6 hours via heelstick, central/arterial line or venipuncture

Title: Direct Peritoneal Resuscitation in Gastroschisis

PI: [name]

Sponsor: UAMS

per NICU standard practice for 24 hours after the maximum dialysate infusion volume has been reached, then every 12 hours through Post-Closure Day 1.

Investigational Product

Dianeal PD-2 1.5% is a sterile, nonpyrogenic, hypertonic peritoneal dialysis solution containing dextrose, a monosaccharide, as the primary osmotic agent. Routine peritoneal dialysis in neonates and infants utilizes up to 40 mL/kg of dialysate per dwell. It will be administered via a 10 mm flat JP drain as a bolus infusion every 6 hours until the abdominal wall is closed (generally 3-5 days), but not to exceed 7 days maximum. The initial bolus infusion will be 10 mL/kg of Dianeal 1.5%. If tolerated, each subsequent infusion will be increased by 10 mL/kg of Dianeal 1.5% up to a goal infusion of 40 mL/kg (to a maximum volume of 100 mL) as tolerated.

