All other standard care laboratory tests will be performed at the discretion of treating neonatologists.

Routine daily labs for gastroscisis patients include:

- Complete Blood Count (CBC) with differential
- Magnesium
- Renal function panel (sodium, potassium, chloride, bicarbonate/CO₂, BUN, creatinine, calcium, phosphate, albumin, glucose)

Research Laboratory Tests

Additional research labs for safety monitoring will be drawn via heelstick, central/arterial line or venipuncture per NICU standard practice. The first capture of research labs should coincide with routine labs to avoid repeat blood draws. Up to 2 mL of blood for research may be drawn each day in addition to the routine daily labs.

SoC Group

A research lab for lactate only will be drawn every 24 hrs (\pm 30 minutes) through Post-Closure Day 1.

DPR Group

Additional research labs will be drawn every 6 hrs (\pm 30 minutes) for 24 hours after the maximum dialysate infusion volume is reached, then every 12 hrs (\pm 30 minutes) through Post-Closure Day 1.

Research labs include:

- Lactate
- Sodium
- Potassium
- Glucose

Glucose via heelstick, central/arterial line or venipuncture per NICU standard practice will also be obtained within 1 hour prior to infusion and 1 hour (\pm 15 minutes) post-infusion for the first day of treatment.

The total amount of blood to be withdrawn per day, accounting for the additional research labs above for safety monitoring, will be up to 3 mL.

Ultrasound

We will perform trans-abdominal ultrasound imaging on all enrolled subjects from the time of abdominal wall closure until feedings have commenced. Additional imaging will be performed if the neonatology team has warranted a stop to feeding the neonate. This noninvasive modality will be used to determine categorization of intestinal motility. Abdominal ultrasound will be performed each morning at the bedside by the PI or other trained study personnel.

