We will document the presence of intestinal motility with continuous recording of ultrasound in all four quadrants for 30 seconds. Clips will be stored from each abdominal quadrant with the linear probe. If bowel motility is not recognized by 3 weeks post-operative, then the imaging will be terminated. A separate computer workstation connected to the image server will be used for image viewing and data analysis. Images and videos will be reviewed for quality and assessment of motility. To assess motility, the investigators will identify all distinct bowel loops visualized in the video clips and count movements in each of the bowel loops identified in the clip to determine a motility count for each quadrant. Videos will be classified as poor, fair or good. Motility will be quantified as the total number of distinct peristaltic movements visualized in each abdominal quadrant over 30 seconds. Cumulative motility (CM) will be

Title: Direct Peritoneal Resuscitation in Gastrochisis

PI: [name]

Sponsor: UAMS

calculated as the sum of motility from all four abdominal quadrants. Mean motility (MM) will be calculated as the mean number of distinct peristaltic movements per patient on each day of life imaged. A global descriptive score of bowel activity will also be assigned for each quadrant with the following categories: no, low, normal, or hyperactive peristalsis [20].

Data to be obtained (No. 1-13 are already obtained and available as part of the neonates' medical records):

All data collected as recorded by the NICU for the Children's Hospital Network Database (CHND) will be reviewed for the research. Data with an asterisks () are not included in the standard CHND database.*

1. Demographics
 - a. MRN, admit date, birth date, re-admission, gender, mother's zip code, birth weight, admit weight, gestation, birth head circumference
2. Transport and admission
 - a. Referral source
 - b. Morbidities and diagnoses present at admission
 - c. Lines, tubes, and drains present at admission
3. Maternal, prenatal, perinatal (This is part of the neonates' medical record and will be abstracted from the neonates chart.)

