- b. X-ray reads daily by radiology
- c. Reason and time of change in feeding regimen
- d. Stool output

15. Adverse events*

- a. The durability of treatment effectiveness as well as potential longer-term adverse events will be assessed via chart reviews of pediatric follow-up visits or follow-up phone calls up to 90 days after discharge.

Timeline

We estimate that after approval, it will take approximately 2-3 years to accrue and follow subjects as a single-site study and 6 months to analyze data and prepare manuscripts.

Calendar of Procedures and Assessments

Assessment	Screening (Day of Birth 0-12 hrs)	Staged Reduction (Day of Birth 0-24 hrs)	Day of Life 1-7	Day of Closure	Post-Closure Day 1	Post-Closure Day 2 until Discharge	Day of Discharge	Post-Discharge Follow-Up (up to 90 days)
Informed Consent	X							
Randomization	X							
Silo/JP Drain placement ¹	X							
Verify lab values for eligibility		X						
Vitals (HR, RR, BP/MAP, SpO2)	X ²	X ²	X ²	X ²	X ³	X ³	X ⁴	
Weight	X	X	X	X	X	X	X	
Routine Labs ⁵	X			X	X	X	X	
Research Labs ^{6,7}	X	X	X	X	X	X	X	
G-tube placement ⁴	X ³							
Instill DPR ⁸	X		X					
Intake/Output		X ²	X ²	X ²	X ³	X ⁴		
Glucose pre- & post-infusion ⁹	X	X	X					
Bedside ultrasound				X		X ¹⁰		
AE assessment ¹¹	X		X	X	X	X	X	
Remove OG-tube & Initiate EBM/Formula ¹						X		
Chart Review or Phone Call							X	

¹ Silo placement only or silo and JP drain placement per randomized group assignment

² Q6 hrs (± 30 min) for 48 hrs after maximum volume, then Q12 hrs (± 30 min)

³ Q12 hrs (± 30 min)

⁴ Per NICU Standard Practice

⁵ All: CBC w/ Diff, Magnesium, Sodium, Potassium, Chloride, Bicarbonate/CO₂, BUN, Creatinine, Calcium, Phosphate, Albumin, Glucose, Q24 hrs (± 30 min)

⁶ SoC Group: Lactate only, Q24 hrs (± 30 min) same time as Routine Lab

⁷ DPR Group: Lactate, Sodium, Potassium, Glucose, Q6 hrs (± 30 min) for 24 hrs after maximum volume, then Q12 hrs (± 30 min)

⁸ DPR Group: Q6 hrs (± 30 min), dwell for 1 hr, then remove excess fluid - 10 mL/kg initial bolus, then increase by 10 mL/kg up to 40 mL/kg (100 mL maximum volume)

⁹ DPR Group only: Glucose within 1 hr prior to every infusion and 1 hr (± 15 min) every post-infusion for the first day (24hrs) of treatment

¹⁰ Daily bedside ultrasound will be performed from post-closure Day 1 to time of full feeds and if feeds are stopped for any reason

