Demographic variables will be assessed for differences between groups. Categorical variables will be examined using Fisher's Exact Test or Chi Square Test. Continuous data will be examined using Students' T-test. All tests will be two-sided assuming a significance level of 5%. The dependent variable will be tested to ensure the assumption of normality is met.

The primary outcome measure is time to full enteral feeds of 100 kcal/kg/day. Using a two-sample t-test, we estimated that a sample size of 20 in each of the two groups will yield at least 80% power to detect a 6-day difference in mean time to goal enteral feeds (100 kcal/kg/day) assuming a common standard deviation of 7 and a two-sided significance level of 5%.

The proposed data analyses and sample size calculations were conducted with the support of statisticians at ACRI using SAS® Software, Version 9.4[24].

Ethical Considerations

This study is to be conducted according to applicable government regulations and Institutional research policies and procedures.

Title: Direct Peritoneal Resuscitation in Gastroschisis

PI: [name]

Sponsor: UAMS

The parent(s)/LAR of each potential subject identified as meeting inclusion criteria for this study will be approached to discuss participation in this study by trained study personnel. The person obtaining consent will go over the informed consent comprehensively with the parent(s)/LAR. The risks and rationale of this study will be outlined and all questions will be answered. The volunteer natures of this project will be emphasized, including uninhibited withdrawal from the study at any time. No coercion or undue influence will be used in the consent process. A copy of the signed consent will be given to the subject's parent(s)/LAR, and the informed consent process will be documented in each subject's research record in a separate process note.

Ways of consenting parent(s)/LAR:

1. Mother or father (if mother and father are married)/LAR consented prenatally in OB/GYN clinic.
2. Mother or father (if mother and father are married)/LAR consented after birth via faxed consent to the OB unit and returned to PI. The faxed consent will then be witnessed by bedside nurse.
 - a. The person obtaining consent will fax a consent form to the OB unit and conduct the consent process conversation by phone once the mother or father/LAR has the form in hand.

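### Time to intestinal motility is cut off at 3 weeks by the imaging rule, but the plan lists no method for continuous data that can use a time known only to exceed 21 days

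*Combined protocol and SAP*

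**What the plan says.** Study Objectives, Primary Objective 1, lists among the secondary outcomes "time to intestinal motility, and total days in the hospital". Neither a starting point for the clock nor the finding that counts as motility is defined for this outcome.

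The Ultrasound section sets a stop, ending imaging on this condition: "If bowel motility is not recognized by 3 weeks post-operative". It also says imaging runs "from the time of abdominal wall closure until feedings have commenced", with further scans if feeding is halted. Footnote 10 of the Calendar of Procedures and Assessments differs: "Daily bedside ultrasound will be performed from post-closure Day 1 to time of full feeds". The Schedule of Procedures and Assessments (Post-Closure Day 2 until Day of Discharge) also runs to full feeds.

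Data Analysis names Fisher's exact or chi-square for categorical variables. For the rest: "Continuous data will be examined using Students' T-test". That paragraph opens with "Demographic variables will be assessed for differences between groups" and closes with a normality check that has no stated fallback. The section contains no rank or survival method, no censoring rule and no test tied by name to a secondary outcome.

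**The concern.** An infant without recognized motility at 3 weeks is right-censored by design: the time is above 21 days and otherwise unknown. A t-test needs a number for every infant, so the analyst must leave the infant out or enter a substitute, most obviously 21. Leaving out removes the slowest recoveries, and they come mostly from the slower arm. Entering 21 understates them.

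The documents make such infants plausible. Complex gastroschisis is recorded at silo placement but is not an exclusion, and Appendix B plans for failure to tolerate diet 3 to 4 weeks after closure. If the handling is not fixed beforehand, it will be chosen after the data are seen, in a trial of 40 for which no blinding is described. The stakes are modest: one secondary outcome and an unknown amount of censoring.

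**Working it through.** **Plan's own figure.** There is none for this outcome. The only power statement in Data Analysis concerns time to full feeds and is a separate matter.

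**Inputs from the documents.** Imaging cut-off 3 weeks, taken as 21 days after closure; 20 infants per arm; two-sided 5%. Nearest stand-in for location: feeds start on average 7 days after closure (Standardized treatment algorithms, item ii).

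**Assumptions, none from the documents.** Log-normal times; SoC (mean m, SD s) of (7,5), (7,7), (10,7) or (10,10) days; DPR times 0.6 of SoC times.

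**Formulas.** σ² = ln(1 + (s/m)²), μ = ln m − σ²/2, z = (ln 21 − μ)/σ.
- Share past 21 days: 1 − Φ(z)
- Mean if those infants are dropped: m·Φ(z − σ)/Φ(z)
- Mean if 21 is entered: m·Φ(z − σ) + 21·(1 − Φ(z))

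**Example, (7,7).**
- SoC: σ = √ln 2 = 0.833, μ = 1.599, z = (3.045 − 1.599)/0.833 = 1.736. Share past 21 days: 4.1%. Dropped mean: 7 × 0.817/0.959 = 5.96. Capped mean: 5.72 + 21 × 0.041 = 6.58.
- DPR (mean 4.2, SD 4.2): 0.9% past 21 days, dropped mean 3.97, capped mean 4.13.
- True difference 7 − 4.2 = 2.8 days; dropped 5.96 − 3.97 ≈ 2.0; capped 6.58 − 4.13 ≈ 2.5.

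| SoC mean, SD | SoC past 21 d | DPR past 21 d | True diff. | Dropped | Capped at 21 |
|---|---|---|---|---|---|
| 7, 5 | 2.1% | 0.2% | 2.8 | 2.4 | 2.7 |
| 7, 7 | 4.1% | 0.9% | 2.8 | 2.0 | 2.5 |
| 10, 7 | 6.8% | 1.1% | 4.0 | 2.9 | 3.5 |
| 10, 10 | 9.6% | 2.7% | 4.0 | 2.2 | 3.1 |

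Simulation agrees within its noise (capped: 2.4 to 2.7 and 3.1 to 3.6).

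**Chance that the question arises.** P(at least one of 40 passes 21 days) = 1 − (1 − p_SoC)^20 × (1 − p_DPR)^20 = 38%, 64%, 80% and 92% in the four scenarios.

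**Other directions.** With no effect the difference stays at zero under either handling. With DPR slower (ratio 1.33, SD 0.5 to 1.0 times the mean), dropping leaves 55% to 86% of the true harm at SoC mean 7 and 39% to 64% at mean 10.

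**Power, 20 per arm, 4,000 simulated trials per scenario, ratio 0.6.**

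| SoC mean, SD | t-test, no cut | t-test, dropped | t-test, capped | Wilcoxon, no cut | Wilcoxon, unresolved tied last |
|---|---|---|---|---|---|
| 7, 5 | 0.61 | 0.61 | 0.63 | 0.67 | 0.67 |
| 7, 7 | 0.37 | 0.37 | 0.41 | 0.45 | 0.45 |
| 10, 7 | 0.62 | 0.57 | 0.65 | 0.67 | 0.67 |
| 10, 10 | 0.39 | 0.35 | 0.44 | 0.47 | 0.47 |

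Dropping costs 0 to 5 points here, and up to about 6 over repeated runs. Capping costs none. The Wilcoxon test loses nothing to the cut, because the unresolved infants still rank behind everyone else. It already leads the uncut t-test by 5 to 8 points, and that lead comes from the assumed skew.

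**The case against.** Four points can be made for the plan.

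1. Data Analysis never says that this outcome goes to a t-test, and the t-test sentence sits in a paragraph that starts with demographics. A reader might infer that the t-test is prescribed; the documents do not say so. This stands. But if the natural reading is rejected, the outcome has no stated analysis at all, and the repair is the same.

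2. Few infants may reach the stop. Feeds begin only after a bowel movement has occurred, on average 7 days after closure, so 7 days is probably a high stand-in for motility. The 10-day mean has no source. At mean 7, fewer than one SoC infant in 20 is expected past 21 days (20 × 0.041 = 0.8). This stands, with the reservation that complex cases are enrolled and the tail is unknown.

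3. Entering 21 is milder than dropping, and the plan chooses neither. This also stands. A capped mean is a legitimate restricted mean to 21 days if it is declared as one; here nothing is declared.

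4. A reader might infer that the 3-week rule costs substantial power and that a rank test recovers it. The uncut t-test column does not support that: at the assumed means of 7 to 10 days the cut accounts for little of the gap, and none of it at mean 7.

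None of these supplies the missing rule.

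**Conclusion.** The point holds as a minor one. The 3-week stop right-censors a named secondary outcome, and the only listed method for continuous data cannot use a censored time.

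Under the assumed log-normal scenarios, dropping unresolved infants removes about 14% to 44% of a true difference (2.4 of 2.8 days kept at best, 2.2 of 4.0 kept at worst). Entering 21 removes about 4% to 23%. All of this rests on assumed distributions, and the effect is small if few infants reach 3 weeks.

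A reader might infer that the plan necessarily understates a benefit of DPR. The documents do not support that, because it presumes a benefit. With no effect there is no bias, with harm the harm is understated, and if DPR left more infants unrecovered, dropping them could hide it.

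A second gap compounds the first. If imaging stops when feeds begin, an infant fed before motility is recognized has no event, and follow-up ended because the infant was recovering. Censoring that infant at the last scan as though the stop were unrelated to motility would be informative censoring.

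**What to change.** In Data Analysis, state that time from abdominal closure to first recognized motility is compared by a Wilcoxon rank-sum test, with infants unresolved at 3 weeks tied at the last rank. The alternative is Kaplan-Meier and log-rank with those infants censored at 21 days. Report medians, and the number unresolved at 3 weeks in each arm.

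Define the scan finding that counts as recognized motility. Reconcile the imaging stops in the Ultrasound section, calendar footnote 10 and the Schedule of Procedures and Assessments. State separately how an infant is handled whose imaging ended because feeds began, and do not treat that infant as non-informatively censored.

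The analysis change is a sentence or two and needs no new data; the definition and the reconciled stop are short text edits. The price is that results are ranks or medians, not a mean difference in days.
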